16.3.4. SENSITIVITY ANALYSIS OF OTHER EFFICACY VARIABLES

Sensitivity analysis with no data imputation, including only patients with data collected at the required visit while still on randomized treatment at scheduled visit, or at end of study visit within the visit window will be performed on the health index and VAS score for EQ-5D-5L questionnaire and analyzed using ANCOVA approach, as described in section 16.1.3 of the SAP.

Time to first moderate or severe COPD exacerbation will be analyzed using Cox proportional hazards Regression model as described in section 16.3.3.

16.4. EVALUATION INCLUDING EXCLUDED SITES

Site [REDACTED] was removed from the mITT. As a check of the impact of this exclusion, the following analyses will be performed in the mITT Extended dataset.

- Analysis of FEV₁ AUC₀₋₁₂
- Analysis of peak FEV₁
- Analysis of E-RS total score
- Analysis of SGRQ total score
- Analysis of morning trough FEV₁
- Responder analysis of SGRQ total score

17. SAFETY OUTCOMES

All outputs for safety outcomes will be based on the SAF set. There will be no statistical comparisons between the treatment groups for safety data, unless otherwise specified with the relevant section.

17.1. ADVERSE EVENTS

Adverse Events (AEs) will be coded using MedDRA central coding dictionary. The version of MedDRA to be used will be specified prior to database lock.

Treatment-emergent adverse events (TEAEs) are defined as AEs that started or worsened in severity on or after the first dose of study medication. Laboratory or ECG findings from procedures or samples drawn prior to the first doses of study medication that are assessed/overread after randomization will be considered pre-treatment.

In the case where it is not possible to define an AE as treatment-emergent or not, the AE will be classified by the worst case; i.e. treatment-emergent.

See Appendix 2 for handling of partial dates for AEs.

An overall summary of number of patients within each of the categories described in the subsection below, will be provided as specified in the shells. In addition, the number of patients with each of the following AE events will be presented by SOC and PT and summarized by treatment group and different period (i.e. Treatment period, Follow-up and Overall):

- TEAE
- TEAEs causally related to study medication

- Serious TEAEs
- TEAEs with an outcome of death
- TEAEs leading to discontinuation of blinded study medication
- TEAEs leading to withdrawal from study (TEAEs with a diagnosis of COVID-19, TEAEs with no diagnosis of COVID-19)
- TEAEs by maximum severity

AEs will be identified by using the “Adverse Events” page of the eCRF. Listings will include TEAEs and Non-TEAEs.

Treatment period is defined as the period from the date and time of first dose up to the date and time of last dose.

Follow-up is defined as the period from after the date and time of last dose up to the last date recorded on the study.

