| Efficacy Assessments and Associated Procedures | V0 | | V1 | V2 | V3 | V4 | V5 | | | | |
| Patient Contact Day Prior to Spirometry Visits ⁸ | | | X | X | X | | X | | | | X |
| COPD Exacerbation Assessment | | | X | X | X | X | X | X | | | X |
| Spirometry Training ⁹ | X | | X | X | X | | X | | | | |
| Spirometry (pre-dose) ¹⁰ | | | X | X | X | | X | | | | |
| Spirometry 0-4 hours post dose ¹⁰ | | | X | X | | | X | | | | |
| Spirometry 0-12 hours post dose ¹⁰ | | | | | X | | | | | | X |
| Health Outcomes ¹¹ | | | | | | | | | | | |
| SGRQ | | | X | X | X | | X | | | | |
| EQ-5D-5L | | | X | | X | | | | | | |
| BDI | | | X | | | | | | | | |
| TDI | | | | X | X | | X | | | | |
| Healthcare Utilization Assessment | X | | X | X | X | X | X | X | X | X | X |
| Patient Perception Survey | | | | | | | | | | | X |

Table 3: Schedule of Activities

| Study Assessments and Procedures | Screening 1 day Clinic Visit ¹ | Run-in Period 28 Days ± 4 Days Run-in | Procedures for Patients Completing 24-Weeks of Treatment | | | | | | | Procedures for Early Term/Withdrawal | | | |
|---|---|--|--|------------------------------------|-------------------------------------|-----------------------|-------------------------------------|--------------------------------------|------------------------------------|--------------------------------------|--|----------|--|
| | | | Day 1 (Rand) Clinic Visit ¹ | Week 6 Clinic Visit ^{1,2} | Week 12 Clinic Visit ^{1,2} | Week 18 Phone Contact | Week 24 Clinic Visit ^{1,2} | Follow up Phone Contact ³ | Early Term/Withdrawal ⁴ | Follow up Phone Contact ³ | | | |
| Issue eDiary to Patients Eligible to Enter Run-in | X | | V1 | V2 | V3 | V4 | V5 | | | | | | |
| Assess eDiary and E-RS Compliance (E-RS/EXACT-PRO will be on eDiary) ¹² | | | X | X | X | X | X | X | | | | X | |
| Collect eDiary | | | | | | | | X | | | | X | |
| Safety Assessments | | | | | | | | | | | | | |
| Vital Signs ¹³ | X | | X | X | X | | | X | | | | X | |
| 12-Lead ECG (pre-dose) ¹⁴ | X | | X | X | X | | | X | | | | X | |
| 12-Lead ECG (1.5 hours post dose) ¹⁴ | | | X | X | X | | | X | | | | X | |
| Physical Examination | X | | | | | | | | | | | | |
| AE Assessment | | | X | X | X | X | X | X | | | | X | |
| Laboratory Assessments | | | | | | | | | | | | | |
| Laboratory Tests Haematology, Chemistry (non-fasting), Pregnancy Test (serum) ¹⁵ | X | | X | | | | | X | | | | X | |
| Urine Pregnancy Test for Women ¹⁵ | | | X | X | | | | | | | | | |

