6.1.2 Dosing at Home

Following Visit 1, patients will self-administer their daily morning and evening doses at home at approximately the same times, approximately 12 hours apart, each day for the duration of the study, except for specific clinic visit days when patients will have their doses administered in the clinic.

Prior to Dosing at Home

- Patients in the maintenance LAMA or LABA stratum should take their maintenance LAMA or LABA (and ICS, if applicable) prior to taking blinded study medication.

Blinded Study Medication Administration

- Each patient will follow the Nebulizer Set-Up instructions and blinded study medication label to prepare and self-administer the blinded study medication by inhalation using the reusable study supplied nebulizer attached to the study supplied compressor.

- Blinded study medication nebulization time should be approximately 5 minutes and may not exceed 10 minutes.
- The end time of blinded study medication nebulization is considered to be when a slight sputtering sound from the nebulizer is heard. This will be considered Time 0 for the purposes of scheduling all post-dose study procedures.
- On the evening Prior to the Week 6, Week 12 and Week 24 Visits (or Early Term/Withdrawal visits where 12-hour spirometry will be performed): On a patient paper diary, the patient will record the date, the start time of nebulization, and the end time of nebulization for the evening dose of blinded study medication.

Used Blinded Study Medication

- Patients will be instructed to discard all used ampules of blinded study medication and the open foil pouches that contained the used ampules at home.

Unused Blinded Study Medication

- Patients should be instructed to bring all unused blinded study medication to the clinic at each clinic visit for collection and assessment of medication compliance by the unblinded site staff member.
- If a foil pouch is opened but the blinded study medication is not opened/not used, the patient should seal the opened foil pouch (eg, tape) before returning it to the clinic.

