15.1.1. DERIVATIONS

Compliance with study medication will be calculated on the number of ampules count (total dispensed – total returned) divided by the prescribed number of ampules expressed as a percentage, see calculations below.

Patient should take the study medication twice daily and record it in their e-Diary apart from Week 24 visit when patient’s last dose will be in the morning.

Patients are dispensed ampules at Visit X and return at Visit X+1, however in the eCRF returned ampules will be recorded under Visit X.

- For time interval compliance to study medication will be calculated as follows:

$$\frac{([N \text{ of Ampules dispensed at Visit X}] - [N \text{ of Ampules returned at Visit Y}])}{\text{Denominator1}} * 100$$

Where Denominator1 is calculated with the following rules:

- N_1 = Number of ampules expected calculated based on total N of Ampules dispensed, taking into account 2 ampules per day, apart from last dose date for completed patients where we would only consider 1 ampule per day.
- For non-Week 24 return ampules visit: N_2 = Number of ampules between dispensing and returning visit calculated: $\{[Date \text{ of Visit Y}] - [Date \text{ of Dispensing at Visit X}] + 1\} * 2$.
- For Week 24 return ampules visit: N_2 = Number of ampules between dispensing and returning visit calculated: $\{[Date \text{ of Visit Y}] - [Date \text{ of Dispensing at Visit X}] + 1\} * 2 - 1$.

- If $N_1 \geq N_2$ then Denominator1 = N_2 .
- If $N_1 < N_2$ then Denominator1 = N_1 .
- Overall Compliance to study medication will be calculated as follows:

$$\frac{(\text{N of Ampules total dispensed} - \text{N of Ampules total returned})}{\text{Denominator2}} * 100$$

Where Denominator2 is calculated with the following rules:

- N_1 = Number of days calculated based on total N of Ampules dispensed, taking into account 2 ampules per day, apart from last dose date for completed patients where we would only consider 1 ampule per day.
- N_2 = Number of days between dispensing and returning visit calculated: $\{ \{ [\text{Date of Visit X(n)}] - [\text{Date of Dispensing at Visit 1}] + 1 \} * 2 \} - 1$.
- If $N_1 \geq N_2$ then Denominator2 = N_2 .
- If $N_1 < N_2$ then Denominator2 = N_1 .

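### The SAP closes the AE treatment period at the last dose with no lag, so by-period tables can show events arising within that dose's dosing interval as Follow-up

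*SAP*

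**What the plan says.** SAP 17.1 defines two periods for the AE tables. The first ends at the last dose: "Treatment period is defined as the period from the date and time of first dose up to the date and time of last dose". The second starts at once: "Follow-up is defined as the period from after the date and time of last dose up to the last date recorded on the study". The listed SOC/PT tables are then "summarized by treatment group and different period (i.e. Treatment period, Follow-up and Overall"). The list covers all TEAEs, related, serious and fatal TEAEs, TEAEs by maximum severity, TEAEs leading to study withdrawal, and "TEAEs leading to discontinuation of blinded study medication".

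The TEAE definition has no upper time limit: "Treatment-emergent adverse events (TEAEs) are defined as AEs that started or worsened in severity on or after the first dose of study medication".

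On dosing, protocol 6.1.2 has patients dose at home morning and evening, "approximately 12 hours apart". SAP 15.1.1 makes the Week 24 visit an exception: "Patient should take the study medication twice daily and record it in their e-Diary apart from Week 24 visit", where the last dose is the morning one. The protocol's schedule of activities marks "12-Lead ECG (1.5 hours post dose") at Week 24, and protocol 1.4 schedules spirometry up to 4 hours after that dose.

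**The concern.** A by-period AE table exists to separate events during exposure from events after it. A cut with no lag treats a patient as off drug from the moment the last dose is taken. The protocol does not treat patients that way. Its PK schedule (8.5.10.1) draws samples after the Week 24 dose, at about 1.0 hour at odd-numbered sites and 1.5 hours at even-numbered sites. It also draws an early-termination sample if ensifentrine was received within the last 48 hours.

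What is at stake is how the split tables read. A reaction to the dose that made a patient stop would sit in the Follow-up column of the discontinuation table. A reader would take it for an event that arose after treatment.

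**Working it through.** The plan gives no figure to reproduce here. The check applies the SAP's two definitions as a rule to time points taken from the protocol.

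**Rule as written:** onset at or before the last dose is Treatment; onset after the last dose is Follow-up.

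**Inputs:** a completer's last dose is the Week 24 morning dose (SAP 15.1.1), given in clinic between 6 and 10 AM (protocol 1.4). The ECG is at 1.5 hours, and spirometry runs to 4 hours. The dosing interval is about 12 hours (protocol 6.1.2). The follow-up contact comes 4 to 10 days later (protocol 4.1).

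| AE onset relative to last dose | Date and time, as written | Dates only | Last dose + 24 h |
|---|---|---|---|
| Week 24 dose, 0.5 h before | Treatment | Treatment | Treatment |
| Week 24 dose, +0.25 h | Follow-up | Treatment | Treatment |
| Week 24 dose, +1.5 h (ECG) | Follow-up | Treatment | Treatment |
| Week 24 dose, +4 h (last spirometry) | Follow-up | Treatment | Treatment |
| Week 24 dose, +12 h | Follow-up | Treatment | Treatment |
| Final home evening dose, +10 min | Follow-up | Treatment | Treatment |
| Final home evening dose, next morning (about +12 h) | Follow-up | Follow-up | Treatment |
| Day +4 | Follow-up | Follow-up | Follow-up |
| Day +10 | Follow-up | Follow-up | Follow-up |

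**Choice of lag.** For the Week 24 dose, lags of 0.5, 1 and 2 days classify these time points identically. A 4-day lag also moves the day +4 event into Treatment, and a 10-day lag moves all of them. The Overall column is the same under every lag.

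**Dates or times.** SAP 17.1 says date and time. SAP 6.1 and SAP 14 define the last dose by date, and the AE algorithm in Appendix 2 compares dates. Clinic nebulization start and end times are recorded (protocol 6.1.1), but the SAP does not say which is the time of last dose. Home dose times are written down only around certain visits (protocol 6.1.2 and 8.5.10.2). The documents do not say that AE onset time is collected. So 17.1 names a cut that may not be computable for many home doses, and it gives no rule for a missing time.

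**Scale for a completer.** Nominal doses from Day 1 morning to Week 24 morning: 168 × 2 + 1 = 337. The interval after the last dose is 1/337, about 0.3% of dosing intervals. This is a share of exposure, not of events.

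**The case against.** The strongest reply is that no safety information is lost. TEAEs have no upper time limit, so every event after the last dose keeps its TEAE status and its relatedness, seriousness and discontinuation flags, and is counted under Overall. Safety data are described without between-arm tests unless a section says otherwise (SAP 17). If programming compares dates, the Week 24 clinic hours stay in Treatment. All of this stands, and it confines the point to the Treatment/Follow-up columns.

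Three stronger readings are tempting, and the documents do not support them.

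- A reader might infer that a quarter of the post-dose ECG safety data falls outside treatment, because Week 24 is one of four visits with a 1.5-hour ECG (Day 1, Weeks 6, 12 and 24). That counts visits, not AEs. ECGs are analysed under SAP 17.3 by visit, by shift and by markedly abnormal criteria, none of which uses the AE periods.
- A reader might infer that AEs leading to discontinuation generally land in Follow-up. An event that starts while dosing continues has its onset before the last dose and stays in Treatment. So does a reaction to an earlier dose when the patient is dosed again at the early termination visit, as the protocol asks where possible (7.3.1). The rule moves only events that start after the final dose, which is true by construction.
- A reader might infer a bias between arms or a misreading at peak exposure. The documents give neither AE rates nor a time to peak concentration.

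One could also note that SAP 17.1.2 and 17.1.4 describe the discontinuation and death summaries without mentioning periods. However, the list in 17.1 includes both among the tables split by period.

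**Conclusion.** The point holds in limited form. SAP 17.1 states a rule, rather than leaving a gap, and the rule places events within one dosing interval of the last dose in Follow-up. That covers AEs starting after the Week 24 clinic dose and reactions to a final dose in patients who never dose again, in every SOC/PT table split by period.

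The size in events cannot be computed without AE rates. For a completer the exposure concerned is one nominal interval in 337. The consequence matters more for the by-period discontinuation table, where the reaction to a final dose may be the event of interest.

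The conclusion rests on reading the date-and-time wording literally. Under a date-only comparison the problem shrinks to events starting the day after a last evening dose, but it does not disappear.

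**What to change.** In SAP 17.1, before unblinding:

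- Define the Treatment period as first dose through last dose plus a pre-specified lag covering at least one dosing interval. For example, use 24 hours, or the end of the calendar day after the last dose when the AE time or dose time is missing.
- Start Follow-up after that point.
- State whether nebulization start or end is the time of last dose.
- Use the same cut in every by-period TEAE table, including related and serious TEAEs and those leading to discontinuation.

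The exact lag is a choice; 24 hours is one that covers the interval with margin.

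The cost is a short edit and one derived flag, with no new data. The downside is that a few unrelated events on the day after the last dose move into the Treatment period. The lag does not change one other feature: Follow-up will still pool the 4 to 10 days after a completer's last visit with longer off-drug time in patients who stop early and remain in the study.

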rescue medication use. Permitted rescue and background medications and the condition of their use during the study are described in Section 6.7.2. Prohibited medications and the prohibited time intervals prior to Screening are described in Section 6.7.3.

Patients completing the run-in period and meeting all entry and Randomization Criteria will be randomized. The two different stratification factors will be applied at randomization. Details on blinded study medication and administration are provided in Section 6. The Study Schematic is shown in Section 1.2.

During the treatment period, patients will complete all assessments and procedures as outlined in the Schedule of Activities (SoA, Section 1.3) for 24 weeks. Patients completing treatment will complete a Follow-up within 4 to 10 days of the last scheduled study visit.

Patients meeting the withdrawal criteria during the study or who withdraw from the study for other reasons will be discontinued and requested to complete the Early Termination/Withdrawal Procedures and complete a Follow-up within 4 to 10 days of the Early Termination/Withdrawal Visit.

Patients who permanently discontinue double blind study medication may remain in the study and follow the assessments and procedures as noted in Section 7.2.

Number of Investigators and Study Centers

Approximately 151 Investigators and study centers are expected to participate in this study.

Number of Patients

Approximately 800 randomized patients are planned.

Treatment Groups and Duration

Randomization will be stratified by two different factors: background maintenance LAMA or LABA therapy use (yes or no) and cigarette smoking (current or former). Patients will be randomized active to placebo 5:3 for 24 weeks. The background therapy stratum will be capped at 50%. Patients in the background therapy stratum are expected to continue their background maintenance LAMA or LABA therapy daily throughout the duration of the study, with the exception of withholding 24 or 48 hours prior to spirometry as previously described.

The approximately 800 patients meeting the Randomization Criteria will be randomized to receive the following treatments in a 5:3 ratio:

Treatment Arm 1: Ensifentrine Nebulized Suspension; 3 mg BID

Treatment Arm 2: Ensifentrine Placebo Nebulized BID

Overall, 500 patients will be randomized to ensifentrine and 300 patients will be randomized to placebo.

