Patients completing the run-in period and meeting all entry and Randomization Criteria will be randomized. The two different stratification factors will be applied at randomization. Details on blinded study medication and administration are provided in Section 6.0. The Study Schematic is shown in Section 1.2.

During the treatment period, patients will complete all assessments and procedures as outlined in the Schedule of Activities (Section 1.3) for 24 weeks. Patients completing treatment will complete a Follow-Up within 4 to 10 days of the last scheduled study visit.

Patients meeting the withdrawal criteria during the study or who withdraw from the study for other reasons will be discontinued and requested to complete the Early Termination/ Withdrawal Procedures and complete a Follow-Up within 4 to 10 days of the Early Termination/ Withdrawal Visit.

Patients who permanently discontinue double blind study medication may remain in the study and follow the assessments and procedures as noted in Section 7.2.

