7.2 Study Participation After Discontinuation of Blinded Study Medication

Patients may permanently discontinue blinded study medication before the end of the study if they choose to or at the investigator's discretion.

Patients who permanently discontinue blinded study medication are not required to withdraw from the study unless they test positive for COVID-19 active disease. Patients who have permanently discontinued blinded study medication but do not test positive for COVID-19 active disease and have not withdrawn consent may continue in the study and complete all remaining protocol specified visits.

The Investigator must document the reason for discontinuation of blinded study medication in the eCRF.

Ideally, patients who have permanently discontinued blinded study medication will continue to attend scheduled clinic visits and complete important efficacy and safety assessments. However, if this is not possible then the investigator will encourage the patient to select one of the three options below to participate in as much of the study as they are willing (or able) to participate:

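### SAP 17.1 counts AEs in an uncapped Follow-up period that lasts days in completers and up to about 25 weeks in patients who stop drug and stay, so the column can differ between arms at equal AE rates

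*SAP*

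**What the plan says.** SAP 17.1 lists seven kinds of TEAE table by system organ class and preferred term, including serious TEAEs and TEAEs with fatal outcome. The number of patients with each is "summarized by treatment group and different period (i.e. Treatment period, Follow-up and Overall". The periods are set by the last dose: "Treatment period is defined as the period from the date and time of first dose up to the date and time of last dose", and "Follow-up is defined as the period from after the date and time of last dose up to the last date recorded on the study". SAP section 17 sets no limit on the time after last dose and asks for no person-time or exposure-adjusted rate. Protocol 9.4.2 plans Kaplan-Meier plots for selected AEs, but SAP 17.1 does not repeat them, and they are not tied to these periods.

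How long Follow-up lasts depends on other sections:

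- **Completers.** SAP 15.1.1 refers to the "Week 24 visit when patient’s last dose will be in the morning". Protocol 4.1 adds: "Patients completing treatment will complete a Follow-Up within 4 to 10 days of the last scheduled study visit".
- **Patients who leave the study.** Protocol 4.1 gives them an Early Termination visit and a contact 4 to 10 days later.
- **Patients who stop drug and stay.** Protocol 7.2 says: "Patients who permanently discontinue blinded study medication are not required to withdraw from the study unless they test positive for COVID-19 active disease". Those who have not withdrawn consent "may continue in the study and complete all remaining protocol specified visits". Protocol 7.1 asks sites to try to retain them.

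Protocol 8.7.1 collects AEs and SAEs from first dose through the follow-up contact. The reduced options for off-drug patients differ, however: 7.2.1 lists AEs, while 7.2.2 and 7.2.3 list only SAEs.

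**The concern.** One column pools patients watched for about a week with patients watched for months. A patient watched longer has more chance of being counted, so the column reflects how many patients stopped drug and stayed, and how early, as well as how often events occur. An arm with more such patients could show more serious events after last dose, and a reader could take that for a late or withdrawal effect of treatment.

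Unequal stopping is plausible on the plan's own terms. Under Protocol 11.6.7 a second exacerbation, or a severe one, leads to discontinuation of study treatment, while 7.2 lets the patient remain in the study. The trial also examines whether the drug affects exacerbations. SAP 3.3 drops a non-responder analysis because of what placebo discontinuations might do to it. SAP 16.3.3 already uses log study time as an offset for exacerbation counts; the safety tables have no counterpart.

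**Working it through.** The documents state no figure on this point, so there is nothing to reproduce. The check has three steps.

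**1. Length of Follow-up.** Inputs: nominal Week 24 visit on day 169 (24 × 7 + 1), visit window ±10 days, contact 4 to 10 days later.

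Follow-up days = visit day − last-dose day + (4 to 10)

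| Last dose | Follow-up, nominal visit |
|---|---|
| Day 169 (completer) | 4 to 10 days |
| Day 127 | 46 to 52 days |
| Day 85 | 88 to 94 days |
| Day 43 | 130 to 136 days |
| Day 1 | 172 to 178 days (24.6 to 25.4 weeks) |

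With the visit at day 179 and last dose on day 1, the extreme is 179 − 1 + 10 = 188 days. A patient who takes drug up to an Early Termination visit has 4 to 10 days, like a completer.

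**2. Effect on the percentage counted.** Assume a constant hazard h per week, equal in both arms. A share s stops drug and stays, with a mean of m weeks of Follow-up. Everyone else has 1 week. The SAP counts each patient once, so

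P = (1 − s)(1 − exp(−h)) + s(1 − exp(−hm))

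With h = 0.03 and m = 14, 1 − exp(−0.03) = 0.0296 and 1 − exp(−0.42) = 0.3430:

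- s = 5%: 0.95 × 0.0296 + 0.05 × 0.3430 = 4.5%
- s = 10%: 0.90 × 0.0296 + 0.10 × 0.3430 = 6.1%
- s = 15%: 0.85 × 0.0296 + 0.15 × 0.3430 = 7.7%

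The ratio is 1.35 for 5% vs 10% and 1.69 for 5% vs 15%. For equal shares it is 1.00.

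Over h = 0.01, 0.03 and 0.06, m = 8, 14 and 20, and shares of 5% vs 10%, 5% vs 15% and 10% vs 20%, the ratio runs from 1.22 to 1.93 and the absolute difference from 0.3 to 6.4 percentage points. At h = 0.01, the nearest of these to rarer events such as serious ones, the ranges are 1.25 to 1.93 and 0.3 to 1.7 points. Which arm is higher depends only on which has the larger share.

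These incidence ratios are smaller than the ratios of observation time. Mean Follow-up at m = 14 is 0.95 + 0.05 × 14 = 1.65 weeks at 5% and 0.85 + 0.15 × 14 = 2.95 weeks at 15%. That is a time ratio of 1.79, against 1.69 for patients counted once at h = 0.03.

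**3. What person-time does.** Expected time at risk to first event over a window of w weeks is (1 − exp(−hw))/h. Summed over patients it is P/h, so events divided by time at risk is P/(P/h) = h in each arm. The rate ratio is 1.00 in every scenario.

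The calculation assumes that every event in Follow-up is ascertained. That fits serious TEAEs and deaths. For non-serious AEs, patients under options 7.2.2 and 7.2.3 contribute long windows without listed AE collection, so the artefact is diluted by an amount the documents do not allow to be calculated.

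**The case against.** The strongest case on the other side is that this is a labelling matter in a secondary column. SAP section 17 plans no between-arm safety comparisons unless otherwise specified. An Overall column stands beside the split. SAP 14 summarises exposure, and SAP 9.1 shows drug and study withdrawal by arm with Kaplan-Meier plots, so a reader can see unequal stopping. SAP section 8 leaves table content to output shells that are not in the documents and could hold person-time columns. All of this stands and limits the impact. It does not separate the two kinds of Follow-up, and the SAP text does not require anything that would.

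Some stronger readings are tempting but not supported:

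- **That the column must show more AEs in whichever arm stops drug more.** The driver is stopping and staying. Patients dosed up to an Early Termination visit have a window like a completer's, and under Protocol 7.1.6 active COVID-19 means leaving the study. More stopping with the same stop-and-stay share and timing produces no artefact.
- **That Treatment-period percentages are biased downwards in that arm.** Early stoppers have less time on drug, but those who stop because of an AE have already contributed that AE. The direction is not established.
- **That the ratio of observation times is the ratio of AE percentages.** Patients are counted once and non-serious AEs are not always solicited off drug, so the time ratio overstates it.

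A simple rate for all TEAEs would bring its own error. Off-drug time without AE collection would enter the denominator and understate the rate.

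**Conclusion.** The point holds in a limited form. As written, SAP 17.1 puts windows of about 4 to 10 days and windows of up to about 25 weeks in one Follow-up column, without person-time. Arms can then differ in that column at equal AE rates if the share or timing of stop-and-stay patients differs. Under the assumed equal, constant hazards and unequal shares, the ratio of percentages is roughly 1.2 to 1.9; if shares and timing are equal it is 1.0. The documents give none of the hazards, the shares or the mean time off drug.

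The effect is fullest for serious TEAEs and deaths. It bears on how descriptive safety tables are read, and no hypothesis test is affected. It is worth correcting because it is cheap and these tables are the planned safety comparison.

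**What to change.** In SAP 17.1:

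1. Split Follow-up into time off drug before the patient's last study visit (Week 24, or Early Termination for those who leave the study) and the post-study contact of 4 to 10 days. Define the boundary by the last visit, because Protocol 7.1 asks patients who stop drug to complete the withdrawal assessments promptly even when they stay.
2. Show person-time by arm and period. For serious TEAEs and deaths, give patients with an event per 100 patient-years at risk, with time counted to first event. Give the off-drug rate for all TEAEs only for patients followed with AE collection (full visits or option 7.2.1).
3. Name one source for the last-dose date that divides the periods. SAP 14 uses the Drug Exposure pages, while SAP 9.1 takes medication withdrawal from the End of Treatment page. If the Drug Exposure pages hold only clinic doses, home doses taken after the last clinic dose would fall in Follow-up.

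The cost is SAP wording and a few table columns. The dates are already collected, once the last-dose source is settled. The downside is that off-drug rates will be sparse and, as summaries, rest on a constant hazard.
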